
(formerly HI-FIVES) showed sustained improvements in a key quality metric, caregivers' and patients' experience of care. Based on these results and persistent gaps in caregiver training, VA's Caregiver Support Program is partnering with Function QUERI to plan and conduct a national rollout of the program.

Function QUERI Results to Date

[figure not shown]
The current proposal builds upon and extends work that we began with initial funding of Function QUERI in October 2016. We will continue our focus on the same 3 clinical programs -Group PT, STRIDE, and Caregivers FIRST - because of their importance to VA and Veterans, relevance to our theme, and the opportunity and capability to move each of them to the next phase of implementation. Group PT was implemented at one site as a successful QI initiative: the next step is to implement and evaluate in a diverse group of VAMCs. STRIDE and Caregivers FIRST are each being implemented in stepped wedge cluster randomized trials (CRTs; n=8 VAMCs for each trial) which are ongoing. Although full trial results are not yet available, these EBPs have achieved substantial implementation momentum with national program offices endorsing further spread. STRIDE was named a Gold Status Practice in the 2018 VA Diffusion of Excellence Shark Tank competition and in 2019 endorsed by [name] as one of 3 EBPs in this cohort that should be considered for implementation at all VAMCs. VA's Caregiver Support Program (CSP) has selected Caregivers FIRST for national rollout to all VAMCs to extend the portfolio of services available to caregivers of Veterans as mandated in the MISSION Act. While this endorsement is supportive of implementation, we know that adoption of EBPs rarely happens automatically even when there is policy and stakeholder support. 19 An active approach to implementation is critical to ensure uptake and use of these three EBPs in routine clinical practice.

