
Second, we will employ a **qualitatively driven convergent design** (QUAL + *quan*) in which pre-implementation qualitative data are collected at baseline in parallel with quantitative data in order to explore and understand pre-implementation contextual factors related to differences in site-level adoption, addressing the question: *What baseline organizational and implementation team characteristics are associated with sites that don't meet adoption benchmarks?* All projects will use similar approaches to understand organizational readiness to change, organizational resilience, and other common measures. Data sources will include pre-

implementation quantitative surveys and qualitative interviews at baseline to understand organizational and contextual factors and EHR data to define adoption. Key informants will include members of the implementation team as well as organizational leaders (e.g., chief of staff, facility director). In our ongoing Function QUERI work our richest understanding of context has been through qualitative inquiry, and we will use quantitative data collected via surveys administered to site hospital and service-line leadership and EBP implementation team members as an added dimension for understanding qualitative findings. ^{41,46} In order to increase survey participation, we may offer incentives such as an entry into a raffle for small prizes.

Common measures. Consistent with our framework (Fig. 2) we assert that team factors, environmental context and implementation processes including EBP adaptations are critical factors in influencing implementation outcomes. Our ongoing Function QUERI work has demonstrated heterogeneity in extent of adoption of EBPs designed to promote function and independence. An important component of our proposed work is to explore potential pre-implementation contextual contributors to this heterogeneity. Below we provide an overview of domains and example quantitative measures that will be used across projects. Data from survey measures will be integrated with qualitative data as described above.

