Study design and methods. The Function QUERI team will convene a panel of stakeholders (e.g., clinicians and operations partners) to achieve the following Aim 1 activities: 1) Develop and refine tools and processes to be used in foundational REP activities (e.g. data reports, Office hour calls) and 2) Propose Group PT adaptations that sites may choose to enhance delivery and fit within their context (e.g. "rolling" entry to the program vs. starting new cohorts together; inclusion of a physical therapy assistant in leading group exercises vs. other staff; and patient participation via telehealth vs. in-person). For the CRT addressing Aim 2, 16 VAMCs will be randomized (1:1) to either foundational REP or enREP (Fig. 3). Participating sites must meet the following criteria: 1) Clinical personnel on staff to conduct initial evaluations and lead group classes (e,g, physical therapist, PT assistant, kinesiotherapist): this should include at least 1 primary person and 1 back-up person to cover all aspects of program delivery, 2) Offer outpatient PT service, and 3) Space to conduct group sessions (if implementing in-person Group PT classes). Sites that are currently offering a group class specifically for knee OA will not be eligible to participate. Because rural sites often have fewer PTs and therefore a particular need for strategies to maximize efficiency of delivering these services, at least 25% of sites will be rural. Specifically, we will use the ORH rurality calculator, which pulls data from the Current Enrollment Cube, using closest facility or county/zip code level data to determine percent of rural veterans served by a facility We will use a target threshold of ≥50% rural/highly rural Veterans served by a facility when recruiting sites. If we cannot reach our benchmark (25% of sites) using this threshold, we will then target sites at which 40-50% of Veterans served are

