classified as rural or highly rural. Using methods that have been successful in our prior Function QUERI work, and in partnership with the Physical Medicine & Rehabilitation Service and VISN 6, we will invite participation in the Group PT project in national and regional forums, e.g. monthly PM&R and Chiefs of Staff calls. Randomization will be stratified based on the Complexity Level, where sites 1a, 1b, and 1c are one category and all others (2, 3, CBOCs/Health Care Centers) are the other category (bottom quartile vs. higher; MISSION Act Quality Standard) and rurality, where sites serving ≥50% rural/highly rural Veterans are one category and sites serving <50% rural/highly rural Veterans are another category.

Implementation activities. Foundational REP has been described previously. One component of Foundation REP is the data dashboard, which will assist sites with tracking their own data. The FQ team will use CDW data (e.g., # of consults, # of completed evaluations, etc.) to generate a tool to assist sites with quality improvement efforts. Data will be summarized and free of PHI/PII. Reports will be made available through email to the study sites or via the Group PT SharePoint site (access limited to enrolled sites). *EnREP* begins with the same activities as foundational REP. After 6 months, sites randomized to enREP (n=8) that do not meet adoption benchmarks will receive 6 months of intensified implementation support. Adoption will be defined as delivery of Group PT as a clinical service (delivery of at least 1 Group PT class) and enrollment of at least 5 patients within a 6-month period. Patients must attend at least one Group PT class to count towards enrollment metrics. Additionally, sites randomized to enREP that met adoption benchmarks but do not meet the sustainment benchmark (defined as enrolling 15 new patients between months 7-9), will also receive intensified implementation support for the remainder of the study period. Higher intensity strategies will consist of calls between site implementation teams and a Function QUERI facilitator every 2-3 weeks to promote interactive problem solving in the context of a supportive interpersonal relationship. For the quantitative surveys that are completed twice by participating VA staff, (in the pre-implementation phase at baseline and post-implementation phase at 12 months) we will offer a raffle for small prizes (\$30-\$50) as an incentive to increase survey completion.

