Patient sample. Patients will be eligible for the Group PT if they have a clinician diagnosis of symptomatic knee OA. Participants will not be included if they have knee pain from another condition, have substantial fall risk, or have other co-occurring health conditions that would make participation in a group exercise class unsafe.

Outcomes. Implementation Outcomes: Implementation adoption will be defined as delivery of Group PT as a clinical service (delivery of at least 1 Group PT class) and enrollment of at least 5 patients within a 6-month period. Patients must attend at least one Group PT class to count towards enrollment metrics. **Penetration** (primary implementation outcome) will be defined as the average number of patients enrolling in the EBP on a monthly basis. **Fidelity** will be defined as the average number of sessions attended by patients who enroll in the EBP. We will also assess the number of referrals to the program, along with the proportion of referrals that result in patients enrolling in the program and reasons for failure to enroll. These metrics will be assessed at 6 months and 12 months (primary) following the initiation of the implementation period.

Effectiveness Outcomes/Quality Metrics will be collected by the physical therapist (e.g., via pen and paper or VA approved survey platform such as VA Qualtrics Research) and documented as health factors in the EHR (within a standardized clinic note template developed by the Function QUERI team), during every group PT class (six total). (*Note: Qualtrics is commercially available and the only approved instance for VA use is the VA Qualtrics Research listed in the ATO.*) These patient-level measures focus on functional outcomes and experience of care, in alignment with the CMS Meaningful Measures Framework, including the Patient-Reported Outcomes Measurement Information System (PROMIS), 30-second chair stand,

maximum pain during the chair stand test on a numeric rating scale (0-10) and patient satisfaction.⁷²⁻⁷⁴ We will continue to track patient outcomes beyond the 12-month formal engagement with enrolled sites to monitor continued progress with Group PT delivery. We may also generate additional data reports for sites to support program sustainment. As outlined above (Group PT Implementation Activities), these reports will be free of PHI/PII and made available through email or via the Group PT SharePoint site (access limited).

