Analyses. To address the question: Are there differences in implementation outcomes (adoption, penetration, fidelity) at 6 and 12 months between arms? We hypothesize that sites randomized to enREP will have superior implementation outcomes, including higher adoption, penetration and fidelity, compared with foundational REP sites at 12-months. We will use generalized linear models⁷⁵ to examine the effect of foundational vs. enREP on implementation outcomes at 12-months. The main predictors of interest will be Foundational REP vs. enREP and stratification variables for the Complexity Level, where sites 1a, 1b, and 1c are one category and all others (2, 3, CBOCs/ Health Care Centers) are the other category (bottom guartile vs. higher) and Rurality, where sites serving ≥50% rural/highly rural Veterans are one category and sites serving <50% rural/highly rural Veterans are another category. We will examine how implementation outcomes change over time using descriptive methods (e.g. plots, descriptive statistics, subgroups). To address the question: What are effectiveness outcomes (function, pain) at implementing sites? We will describe effectiveness/quality outcomes for patients who enroll in the Group PT program, overall and by study arm. We will calculate descriptive statistics for all visits, and change outcomes, among patients who have data from the first and last visits. Qualitative data collection and approaches to data integration are described previously.

Sample size estimate. Sample size calculations were conducted for the implementation outcomes at 12-months. Using a two-sided t-test based on a sample size of 16 sites (8 foundational REP and 8 enREP), a type-1 error rate of 5%, we will have 80% power to detect an effect size difference of 1.5 and 90% power to detect an effect size difference of 1.7 between arms. For the primary penetration outcome, assuming standard deviations ranging from 1.5 to 2.5 based on data of number of new patients per month over a 1-year period of implementation of Group PT in Durham, these effect size differences correspond to differences in mean number of initiators per month ranging from approximately 2.3 to 3.8 between arms for 80% power and 2.6 to 4.3 for 90% power.

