With respect to computer based records, the following practices are followed: (1) All research data are stored on VA-administered servers which are physically secured in a Durham VAHCS server room; (2) Individual computer accounts, password protected, are issued to staff members; and (3) Access to computer data is granted by OI&T personnel after confirming appropriate documentation through the IRB, per ADAPT policies. Utilization and other patient data will be downloaded directly from national files to the Durham HSR&D ADAPT servers or stored in the secure VINCI environment. Of study personnel, only the study Statisticians or other designated personnel will have access to the patient data, which will not be moved from this secured environment.

The key linking the identifiers to the providers' identifying information will be stored in a password protected electronic database and maintained on a password protected VA server, with access only available to approved study staff and investigators.

Withdrawal of Participants

N/A

Data Analysis and Statistical Considerations

The individual projects' sample size determination and analysis plans are as follows below. The data will be analyzed on SAS and SQL local servers (see Location of Data on p. 29) and in the secure VINCI environment by study statisticians and other relevant study team members listed on the IRB-approved study staff listing.

Group PT sample size estimate. Sample size calculations were conducted for the implementation outcomes at 12-months. Using a two-sided t-test based on a sample size of 16 sites (8 foundational REP and 8 enREP), a type-1 error rate of 5%, we will have 80% power to detect an effect size difference of 1.5 and 90% power to detect an effect size difference of 1.7 between arms. For the primary penetration outcome, assuming standard deviations ranging from 1.5 to 2.5 based on data of number of new patients per month over a 1-year period of implementation of Group PT in Durham, these effect size differences correspond to differences in mean number of initiators per month ranging from approximately 2.3 to 3.8 between arms for 80% power and 2.6 to 4.3 for 90% power.

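### Does taking the Group PT standard deviation from a single site (Durham) undermine the stated detectable differences in patients per month?

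*Combined protocol and SAP*

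**What the plan says.** Under Implementation Project 1 (Group PT for Knee OA), the design paragraph states that "16 VAMCs will be randomized (1:1) to either foundational REP or enREP". The primary implementation outcome, penetration, "will be defined as the average number of patients enrolling in the EBP on a monthly basis", with 12 months as the primary time point. Each site therefore contributes one value.

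The sample size estimate uses a two-sided t-test at 5% with 8 sites per arm. It gives effect sizes of 1.5 for 80% power and 1.7 for 90% power. It then converts these to patients per month, "assuming standard deviations ranging from 1.5 to 2.5 based on data of number of new patients per month over a 1-year period", and arrives at roughly 2.3 to 3.8 (80%) and 2.6 to 4.3 (90%). The same text stands under Data Analysis and Statistical Considerations, where the SD is again "based on data of number of new patients per month over a 1-year period of implementation of Group PT in Durham".

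Function QUERI Results to Date records that Group PT had been implemented "at one site as a successful QI initiative: the next step is to implement and evaluate in a diverse group of VAMCs". The Common measures paragraph of the Implementation Core section adds that the program's ongoing work "has demonstrated heterogeneity in extent of adoption of EBPs", without singling out Group PT.

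**The concern.** The t-test compares 8 site averages with 8 site averages, so its denominator is the spread of those averages between sites in the same arm. Durham supplies one site average. One value leaves no degrees of freedom for variation between sites, however the 1.5 to 2.5 was derived from it. The natural reading is that the range describes month-to-month variation within Durham, which is a different quantity, though the plan does not say so.

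What is at stake is the plan's only statement, in patients, of what the primary Group PT comparison can detect. If sites differ more than 1.5 to 2.5 per month, the trial can detect only larger differences than stated. If they differ less, it can detect smaller ones. The plan deliberately recruits a mix of complexity levels and rural sites, so a wide spread is conceivable. STRIDE makes the contrast visible: its SD cites preliminary data from ongoing work, and the ongoing STRIDE trial covers 8 medical centers.

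**Working it through.** **Inputs.** 8 and 8 sites, two-sided 5% t-test, effect sizes 1.5 and 1.7, SD 1.5 to 2.5 per month (Group PT sample size estimate). Benchmarks from Implementation activities: adoption requires "enrollment of at least 5 patients within a 6-month period"; sustainment is "defined as enrolling 15 new patients between months 7-9".

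**1. Standardized power.** Noncentral t with 8 + 8 − 2 = 14 degrees of freedom and noncentrality d × √(8 × 8 / 16) = 2d.

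- d = 1.5: power 79.7% (plan: 80%).
- d = 1.7: power 88.5% (plan: 90%).
- Exact d for 80% and 90%: 1.507 and 1.745, which agree with the plan's values at one decimal.

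No SD enters this step.

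**2. The plan's conversion.** Difference = d × SD.

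| | SD 1.5 | SD 2.5 |
|---|---|---|
| d = 1.5 | 2.25 (plan 2.3) | 3.75 (plan 3.8) |
| d = 1.7 | 2.55 (plan 2.6) | 4.25 (plan 4.3) |

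All four figures reproduce.

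**3. What Durham could contribute.** Assume that 1.5 to 2.5 is Durham's month-to-month SD and that months are independent. Its share of the SD of a 12-month average is then 1.5/√12 = 0.43 to 2.5/√12 = 0.72. With a true between-site SD τ, the total is √(τ² + w²/12), where w is the monthly SD. For τ = 2 this is 2.05 to 2.13. Nearly all of it is τ, which Durham cannot supply.

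**4. Sensitivity to the unknown SD.** The values of 1, 3 and 4 are assumptions; the documents give no between-site figure.

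| SD | 80% power (1.507 × SD) | 90% power (1.745 × SD) |
|---|---|---|
| 1 | 1.5 | 1.7 |
| 1.5 | 2.3 | 2.6 |
| 2.5 | 3.8 | 4.4 |
| 3 | 4.5 | 5.2 |
| 4 | 6.0 | 7.0 |

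**5. A plausibility check from the plan's own benchmarks.** These equal 5/6 = 0.83 and 15/3 = 5 patients per month. If site averages were spread evenly over 0 to 5 (assumption), the SD is 5/√12 = 1.44 and the detectable differences are 2.2 and 2.5, close to the plan's lower figures. Spread evenly over 0 to 10 (assumption), the SD is 10/√12 = 2.89 and the differences are 4.3 and 5.0, above its range. An SD of 4 needs an even spread 4 × √12 = 13.9 per month wide, so it is an outer bound.

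**6. The planned model.** The analysis adjusts for complexity and rurality, so the relevant SD is the residual one after those two variables. That can only help to the extent that they explain enrollment. The cost is 2 degrees of freedom: with 12, power at 1.5 and 1.7 is 78.6% and 87.7%.

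**The case for a change.** The strongest case for a change is that pointing to data tells the reader the range has empirical support for this comparison, which it does not have. The difference of 3.8 per month has about 81% power if the SD is 2.5, but 65% at SD 3 and 42% at SD 4. Someone reading a null result against the planned 3.8 could conclude too much. Correcting it would cost a sentence in two places.

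Part of this stands. No section gives a between-site SD, an intraclass correlation or a multi-site source for Group PT. The rest does not lead to a revision. The plan does not claim that Durham measures spread between sites. It says it is assuming a range, does not explain how the range was reached, and calls the differences approximate. The SDs of 3 and 4 have no better source than 1.5 to 2.5, and the check tied to the plan's own benchmarks over 0 to 5 falls near its lower end, although an even spread is itself an assumption. A null result would be judged on the residual spread that the model estimates from the 16 sites, not on the planning SD. The report of uneven adoption concerns the program's work in general and gives no size for Group PT.

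The gap between 1.7 and the exact 1.745 is ordinary rounding at one decimal. The shift from 4.3 to 4.4 at SD 2.5 has the same cause.

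**Conclusion.** The observation is correct but calls for no change. One site cannot estimate the within-arm, between-site SD, so 2.3 to 3.8 and 2.6 to 4.3 patients per month hold only if that SD lies between 1.5 and 2.5. Nothing in the documents shows that it lies elsewhere, and the direction of any error is unknown. A reader who prefers another SD can scale directly: about 1.5 × SD for 80% power and 1.7 × SD for 90%.

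The standardized statement (79.7% and 88.5% by exact calculation, against 80% and 90%) is independent of the SD. The number of sites, the randomization, the outcome, the test and the model would all stay the same under any rewording. Without a multi-site source, a revision would replace one assumed range with a broader assumed range and alter no result. These conclusions rest on the 8 versus 8 t-test with one value per site, and on the absence of a Group PT between-site variance anywhere in the documents.
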